7.1.1 Dosing Criteria

All patients must meet the following criteria before each dose, based on the most recent laboratory testing:

- ANC $\geq 1.0 \times 10^9/L$
- Hemoglobin ≥ 7.5 g/dL
- Platelet count $\geq 75 \times 10^9/L$ [$\geq 25 \times 10^9/L$ in patients with known lupus-related immune thrombocytopenia]
- AST and ALT ≤ 3 x ULN and bilirubin < 2 x ULN (except for Gilbert's syndrome where bilirubin will not be used to hold dosing)
- Non-ISR AEs \leq Grade 2

7.1.2 Administrative Site

A different injection site should be used for each administration. If sites are to be rotated (i.e., 4 abdominal quadrants), a minimum of 4 weeks should separate injections to the same site.

7.1.3 Monitoring of Dose Administration

Systemic injection reactions have been observed in healthy volunteer studies with KZR-616; the following guidance is based on these known experiences.

In KZR-616-001, 4 of 12 healthy volunteer subjects who received 60 mg KZR-616 SC experienced a "systemic drug reaction" consisting of hypotension, tachycardia, nausea, vomiting, rigors, and chills, associated with an acute phase-like response, including

leukocytosis and elevated C-reactive protein (CRP), which occurred approximately 8 to 12 hours after dosing.

Using dual proteasome inhibitors as a reference point, systemic injection reactions included a number of signs and symptoms including fever, chills, myalgia, facial swelling or flushing, vomiting, weakness, hypotension, chest tightness, and shortness of breath, as well as abnormalities in laboratory values (e.g., creatinine, transaminases) and blood pressure.^{43, 44} However, the relative roles of the immunoproteasome versus constitutive proteasomes to these specific events are not known. The individual signs/symptoms of systemic injection reactions must be reported as AEs of special interest within 24 hours in the AE eCRF (RAVE) (refer to [Section 10.5.1](#)).

With other proteasome inhibitors, prophylactic measures have been demonstrated to reduce the incidence and severity of infusion-related reactions. Therefore, upon the development of signs and/or symptoms suggestive of a systemic drug reaction, the following interventions are suggested:

- Supportive measures, including the administration of oral and/or IV fluids, antiemetics, acetaminophen, antihistamines and/or systemic corticosteroids (e.g., prednisone 25 mg – equivalent to 4 mg of dexamethasone)
- Collection of serum and/or plasma samples for analysis of potentially elevated levels of cytokines, histamines, etc.
- For patients who develop signs and/or symptoms that may be consistent with a cardiac etiology (e.g., hypo- and/or hypertension, tachycardia, arrhythmia, or abnormal cardiac enzymes), the following should be obtained to rule out cardiac toxicity which has been described with proteasome inhibitors:
 - Serial ECGs, cardiac enzymes (e.g., creatine kinase MB [CK-MB], troponins, B-type natriuretic peptide [BNP]) to rule out myocardial infarction
 - Echocardiogram, unless heart failure can otherwise be ruled out by the preceding investigations
- Prophylactic measures may be considered at the time of the first dose, or with subsequent doses if signs and/or symptoms consistent with a systemic drug reaction develop, including:
 - Fluid hydration, e.g., 30 mL/kg orally at least 48 hours prior to dosing; and/or 250 to 500 mL IV after dosing if symptoms are present
 - Antiemetics, acetaminophen, and antihistamines
 - Systemic corticosteroids (e.g., dexamethasone 4 mg or prednisone 25 mg) prior to subsequent doses. Use of systemic corticosteroids should be discussed in advance with the medical monitor as their use could confound efficacy assessments.

7.1.4 **Dose Modification Guidelines for KZR-616**

Dose Reductions

During Phase 1b and Phase 2, patients who experience a KZR-616-related AE, not otherwise subject to Individual Stopping Rules ([Section 9.1](#)), are permitted to undergo dose reduction of 15 mg for subsequent doses at the discretion of the investigator and with medical monitor and/or sponsor approval.

- Patients must continue to fulfill the Dosing Criteria in [Section 7.1](#) prior to each dose
- If the AE does not recur at the lower dose level for at least 2 doses, the original dose may be resumed with medical monitor and/or sponsor approval. If the AE then recurs, dose reduction may be attempted once more with medical monitor and/or sponsor approval. Only one attempt to resume the original dose is allowed per patient
- If the AE recurs at the reduced dose level with the same grade, it should be considered whether or not KZR-616 must be permanently discontinued

Otherwise, intra-patient dose escalations are not allowed.

Missed Doses

Patients who do not fulfill Dosing Criteria ([Section 7.1](#)) may miss up to 2 consecutive doses in Phase 1b or Phase 2 or patients may miss up to 4 total doses in Phase 1b or up to 6 total doses in Phase 2 for any reason (e.g. AE, scheduling, emergency). Upon resumption of dosing, subsequent doses should be timed according to the original dosing schedule based on Day 1. Patients who cannot resume dosing within 2 weeks of the first missed dose or who miss more than 4 total doses in Phase 1b or 6 total doses in Phase 2 must permanently discontinue KZR-616 unless the doses in question were missed based on Study Stopping Rules ([Section 9.1](#)). If doses were missed due to implementation of Study Stopping Rules, then the patient should be discussed with the medical monitor to evaluate if KZR-616 should be discontinued. Any dose modifications should be discussed with the medical monitor and documented in the eCRF.

If study medication is permanently discontinued due to an AE, standard therapy and planned assessments (see Schedule of Assessments, [Section 14.1](#), Appendix A, and [Section 14.2](#), Appendix B, for Phase 1b and Phase 2, respectively) should continue for the protocol specified time period.

7.2 **Prior and Concomitant Medications**

A concomitant medication is any prescription or over-the-counter preparation, including vitamins and supplements. Any concomitant therapies must be recorded on the eCRF. Except as described below, prior and concomitant medication use will be recorded for the 60 days prior to screening until the last follow-up visit.

All prior SLE treatment (e.g., immunosuppressants, antimalarials, biologics) will be recorded, including corticosteroid use, from at least the previous 24 weeks prior to screening. When possible, all prior biologics should be recorded.

SLE Disease-Related Concomitant Medications

Patients should continue all concomitant medications related to SLE therapy throughout the study, as outlined in Inclusion/Exclusion Criteria (Section 5.2), this section (Section 7.2), and Table 3.

- All immunosuppressant therapies and antimalarial agents should be continued at a stable dose except when change is deemed necessary by the treating physician or clinical investigator, or if access is limited due to supply issues (see also Section 7.2.2).
- In Phase 1b, if the baseline prednisone dose is ≥ 10 mg/day, tapering is strongly encouraged, and at the investigator's discretion. However, stable prednisone dose is required between Week 9 and Week 13.
- In Phase 2, if the baseline prednisone dose is ≥ 10 mg/day, tapering is strongly encouraged, and at the investigator's discretion to a goal of prednisone ≤ 10 mg/day (or prednisone equivalent) by Week 16. Stable prednisone dose is preferred between Week 16 and Week 24.
- Prednisone (or other corticosteroid) can be initiated or increased to treat a non-renal SLE flare when deemed necessary by the treating physician or clinical investigator.
- Intra-articular or intra-bursal corticosteroid injections are permitted when deemed necessary by the treating physician or clinical investigator.

Other Concomitant Medications

Other concomitant therapies for comorbid conditions, such as antihypertensives or lipid lowering agents, are permitted. The patient should be advised to maintain stable dosage regimen for antihypertensive medication(s) (such as angiotensin receptor blocker [ARB]/angiotensin-converting enzyme inhibitor [ACE-I]), lipid lowering agents (such as statins), NSAIDs unless the dosage adjustment is clinically necessary, e.g., to control hypertension or for intolerance.

KZR-616 is a substrate of the P-gp transporter. Given the rapid clearance of the drug (half-life < 2 hours), it is unlikely that inhibitors of P-gp will affect drug exposure. However, no formal interaction studies with P-gp inhibitors have been performed. Therefore, KZR-616 should be administered at least 6 hours before or 4 hours after drugs that are known inhibitors of P-gp (e.g., cyclosporine, atorvastatin, azithromycin, colchicine, omeprazole).

Vaccinations

It is strongly recommended that patients be up-to-date on immunizations per current 2015 ACR guidelines for RA.⁴⁵ Vaccinations received at any time documenting that the patient is up-to-date on vaccines should be recorded in the eCRF.

7.2.1 Excluded Concomitant Medications

The use of any investigational agents or devices is prohibited.

Plasma exchange/plasmapheresis and live-attenuated vaccines are excluded.

Please refer to [Section 14.5](#), Appendix E, for a list of excluded medications and associated wash-out periods.

7.2.2 Required Concomitant Medications

Phase 1b:

Patients should remain stable on their medications during the treatment period, per inclusion and exclusion criteria, [Section 7.2](#), and [Section 14.5](#), Appendix E.

Phase 2:

Patients should remain stable on their medications during the treatment period, per inclusion and exclusion criteria, [Section 7.2](#), (including [Table 3](#)) and [Section 14.5](#), Appendix E.

Permitted therapy for LN for study entry is listed in [Table 3](#) and should include at least one non-corticosteroid immunosuppressant. Additionally, one antimalarial and up to 60 mg prednisone or prednisone equivalent are permitted.

For those on a EuroLupus CYC regimen at study entry, once treatment course is complete (500 mg every 2 weeks for 6 doses, or similar), an appropriate immunosuppressive regimen should be initiated with a goal of stable dosing by Week 16, and stable dosing between Weeks 16 and 24.

Once enrolled, treatment regimens should not be changed except as above (including steroid taper) or for reasons of unavailability. Immunosuppressant(s) should not be added to current regimen except as above after completion of a EuroLupus CYC regimen. Corticosteroids should not be added during the study except when needed to treat an SLE flare, and antimalarials should not be added during the study except when they were previously not available, and then are able to be obtained.

During the study, dose modification is not permitted except for reasons of documented toxicity or unavailability, except for up-titration of immunosuppressive therapy after a EuroLupus CYC regimen, and taper of corticosteroids as below.

Corticosteroids should be tapered as per local standard of care or practice to a goal of ≤ 10 mg of prednisone by Week 16.

Table 3: Permitted LN Medications During Study

Permitted Medications during study	Max dose	Therapeutic Agent Stability prior to Baseline	Required washout if not continued during study, from Baseline
Prednisone (or other corticosteroid)	60 mg qd (or prednisone equivalent)	14 days	6 weeks
Mycophenolate mofetil	N/A	8 weeks	8 weeks
Mycophenolic acid	N/A	8 weeks	8 weeks
Leflunomide	N/A	8 weeks	8 weeks
Azathioprine	N/A	8 weeks	8 weeks
Cyclosporine	N/A	8 weeks	8 weeks
Tacrolimus	N/A	8 weeks	8 weeks
Methotrexate	N/A	8 weeks	8 weeks
Other oral immunosuppressants/ immunomodulators	N/A	8 weeks	8 weeks
EuroLUPUS Cyclophosphamide	500 mg IV q2 weeks, or similar	8 weeks	8 weeks, unless course completed and oral immunosuppressant(s) started; a minimum of 14-days should separate last dose of CYC and first dose of KZR-616
Hydroxychloroquine or other antimalarial	N/A	2 weeks	2 weeks
ARB/ACE	N/A	2 weeks	4 weeks
Topical medications	N/A	2 weeks	2 weeks

Abbreviations: ARB/ACE = angiotensin receptor blocker/angiotensin-converting enzyme

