9.2 Early Withdrawal of Patients from Study

Patients may stop study drug for any of the following reasons:

-
- Patient request/withdraw consent due to an AE
 - Patient request/withdraw consent for any reason other than an AE
 - Patient becomes pregnant
 - Use of non-permitted concurrent therapy
 - Non-compliance with the study drug or study schedule
 - AE of \geq Grade 4
 - Lost to follow-up
 - Occurrence of AEs not compatible with the continuation of patient participation in the study, in the investigator's or sponsor's opinion, or unacceptable to the patient to continue
 - Investigator request
 - Sponsor request

For Phase 1b, patients who do not comply with the protocol or who withdraw consent may be replaced. For Phase 2, only patients who withdraw before the Week14 injection may be replaced.

Patients are free to withdraw from the study at any time without providing reason(s) for withdrawal and without prejudice to further treatment. The reason(s) for withdrawal will be documented in the eCRF. If a patient withdraws consent, all samples obtained will be retained for analysis unless the patient confirms that he or she wishes the samples to be discarded.

Patients withdrawing from the study treatment will be encouraged to complete the Early Withdrawal Visit within 7 days and return for an EOS Visit approximately 12 weeks after receipt of their last dose to complete the final evaluations according to this protocol, particularly safety evaluations. The aim is to record data in the same way as for patients who completed the study.

Reasonable efforts will be made to contact patients who are lost to follow-up. These efforts must be documented in the patient's file.

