11.1.2 Phase 2 Endpoints

Primary Endpoint:

- The number of patients with a 50% reduction in UPCR after 24 weeks of treatment when compared to baseline

Secondary Endpoints:

- Safety and tolerability of KZR-616 as assessed by the incidence, nature, and severity of AEs

-
- The number of patients with a partial renal response (PRR) after 24 weeks of treatment as defined by:
 - a) A 50% reduction of UPCR and/or reduction of UPCR to < 1.0 if the baseline UPCR was < 3.0 or a 50% reduction of UPCR and/or reduction of UPCR to < 3.0 if the baseline was ≥ 3.0
 - b) eGFR of ≥ 60 mL/min/1.73 m² or no worsening of eGFR from baseline of $\geq 25\%$
 - c) No use of prohibited medication
 - The number of patients with a complete renal response (CRR) after 24 weeks of treatment as defined by:
 - a) UPCR of ≤ 0.5
 - b) eGFR of ≥ 60 mL/min/1.73 m² or no worsening of eGFR from baseline of $\geq 25\%$
 - c) Prednisone (or equivalent) < 10 mg
 - d) No use of prohibited medication
 - Time to $\geq 50\%$ reduction in UPCR from baseline
 - Time to CRR
 - Time to PRR
 - Time to UPCR of ≤ 0.5 from baseline
 - The number of patients with UPCR of ≤ 0.5 at 24 weeks
 - The number of patients with daily prednisone (or equivalent) dose ≤ 10 mg
 - Change from baseline in levels of autoantibodies (e.g. ANA, anti-dsDNA) and complement at 24 weeks
 - Changes in corticosteroid use from baseline

Exploratory Endpoints:

- The level of proteasome inhibition in whole blood and PBMCs, as measured by both a cleavable fluorogenic substrate enzymatic assay and a subunit-specific proteasome active site ELISA
- Change from baseline in SLEDAI-2K score, CLASI, and 28 joint count and changes from baseline in laboratory measures
- The proteomic and pharmacogenomic activity of KZR-616 will be assessed through ex vivo analysis of whole blood and PBMC samples
- Serum cytokine levels and circulating leukocytes will be measured in blood samples collected on Day 1 of Weeks 1, 5, 17 and 25

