11.3.5 Criteria for Evaluation – Efficacy Analyses

Phase 2:

Assessment of Primary and/or Secondary Endpoints

Please see [Section 11.1.2](#) for a listing of secondary endpoints for Phase 2.

Rate of renal response will be assessed at 24 weeks. Renal response will be classified as complete, partial [50% reduction in UPCR], or no renal response. Summary statistics (e.g., total number of patients with observed data, mean, median, SD, min, max for continuous endpoints; for binary endpoints: total number of patients observed, number of patients with the event of interest, percent) will be provided by dose in Phase 1b and for all patients combined in Phase 2. The primary efficacy endpoint in Phase 2 is percent of patients with 50% reduction in UPCR after 24 weeks of treatment when compared to baseline. The null hypothesis is that the percentage is $\leq 20\%$; the alternative hypothesis is that the percentage is $> 20\%$. The test of hypotheses will be carried out with an exact binomial test. The KZR-616-002 Statistical Analysis Plan contains details of the planned analysis.

Phase 1b and Phase 2: Exploratory Endpoints:

The efficacy of KZR-616 on SLE will be assessed using changes from baseline in study administered questionnaires/disease assessment tools and changes from baseline in laboratory measures.

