11.3.6 Handling of Missing Data

All withdrawals will be included in all analyses up to the time of withdrawal. Patients who are withdrawn prematurely from investigational product and/or the study will be included in all analyses regardless of the duration of treatment. There will be no imputation for missing data, unless otherwise specified.

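### Phase 2 steroid wording differs between Sections 7.2 and 7.2.2 on renal flare, and the supplied text has no rescue rule for the primary UPCR endpoint, so a patient given new steroid for a renal flare can count as a responder unless the separate SAP says otherwise

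*Combined protocol and SAP*

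**What the plan says.** **Steroid rules.** Section 7.2, in its list of disease-related concomitant medications, states: "Prednisone (or other corticosteroid) can be initiated or increased to treat a non-renal SLE flare". It has no phase limit and does not mention renal flare. Section 7.2.2, under Phase 2, states: "Corticosteroids should not be added during the study except when needed to treat an SLE flare". A later paragraph of 7.2.2 adds that "dose modification is not permitted except for reasons of documented toxicity or unavailability", apart from up-titration after a EuroLupus cyclophosphamide course and steroid taper. The Phase 2 text of 7.2.2 opens with a reference back to 7.2. Phase 2 inclusion criterion 6 makes steroid at entry optional, so patients not taking it can be enrolled.

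**Endpoints.** Section 11.1.2 gives the primary endpoint as "The number of patients with a 50% reduction in UPCR after 24 weeks of treatment when compared to baseline". No medication condition is attached. Partial and complete renal response (PRR and CRR) each require that no prohibited medication was used, and CRR also requires "Prednisone (or equivalent) < 10 mg" (the synopsis allows 10 mg or less).

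**Analysis.** Section 11.3.5 sets a null of at most 20% and says "The test of hypotheses will be carried out with an exact binomial test". Under Section 11.3.6, patients withdrawn early "will be included in all analyses regardless of the duration of treatment", with no imputation unless otherwise specified. Section 9.2 lists "Use of non-permitted concurrent therapy" among the reasons a patient may stop study drug. Section 11.3.5 leaves analysis details to the SAP, and Section 11.3.1 gives the SAP precedence over the protocol.

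**The concern.** Every Phase 2 patient has active nephritis, so a renal flare during treatment is foreseeable. Section 2.2 describes corticosteroid as part of guideline therapy for lupus nephritis. Section 7.1.3, writing about drug reactions, warns that systemic steroid could confound efficacy. There is no control arm in which the effect of added steroid would also appear.

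Sites reading the two sections differently could treat the same renal flare differently. Where steroid is added and UPCR at Week 25 is half its baseline value, the supplied text counts the patient as a success of KZR-616. Compared with scoring rescue as non-response, leaving it unscored can only raise the responder count. Section 2.5 expects pivotal studies in lupus nephritis to follow from the Phase 2 safety and efficacy results, so the count matters even though Section 11.4 says the study is not powered by hypothesis testing.

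**Working it through.** **Step 1: the permissions side by side.**

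| Situation in Phase 2 | Section 7.2 | Section 7.2.2 |
|---|---|---|
| Not on steroid, non-renal flare | start permitted | adding permitted |
| Not on steroid, renal flare | silent | adding permitted |
| On steroid, non-renal flare | increase permitted | dose-change paragraph has no flare exception |
| On steroid, renal flare | silent | dose-change paragraph has no flare exception |

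The second row carries the point. The third row is a separate drafting mismatch of less weight.

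**Step 2: does any other text stop the rescued patient counting as a primary responder?**

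- The prohibited-medication condition belongs to PRR and CRR, not to the primary endpoint. Even there it would not clearly catch steroid, which is absent from Section 7.2.1 and Appendix E and is listed in Table 3 as permitted up to 60 mg daily.
- The prednisone cap belongs to CRR only.
- Section 9.2 concerns stopping study drug. It gives no endpoint consequence.
- Section 11.3.6 concerns withdrawal and missing data. It has no rescue rule.

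Nothing in the supplied text stops it.

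**Step 3: what one patient is worth.** There is no planned figure to reproduce, because the plan states no alpha, no power and no derivation of the sample size. Inputs: n = 20 (Section 5.1) and a null rate of 0.20 (Section 11.3.5). The one-sided exact p-value at r responders is P(X ≥ r) for X ~ Binomial(20, 0.20).

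| Responders | p |
|---|---|
| 7 | 0.0867 |
| 8 | 0.0321 |
| 9 | 0.0100 |

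One extra counted responder crosses an assumed one-sided 5% line between 7 and 8, or an assumed 2.5% line between 8 and 9.

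**Step 4: an illustration of frequency.** The next three inputs are assumptions with no basis in the documents: g, the share entering without steroid (25–50%); f, the share of otherwise non-responders among them given steroid for renal flare (10–20%); s, the share of those who then halve UPCR from baseline (25–50%). If the true response rate is 20%, the counted rate is 0.20 + 0.80 × g × f × s.

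| g, f, s | Counted rate | Mean added responders | P(X ≥ 8) | P(X ≥ 9) |
|---|---|---|---|---|
| no rescue | 0.200 | 0 | 0.032 | 0.010 |
| 0.25, 0.10, 0.25 | 0.205 | 0.1 | 0.037 | 0.012 |
| 0.375, 0.15, 0.375 | 0.217 | 0.34 | 0.050 | 0.017 |
| 0.50, 0.20, 0.50 | 0.240 | 0.8 | 0.083 | 0.032 |

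Mean added responders is 20 × 0.80 × g × f × s; for the last row, 20 × 0.04 = 0.8. With s = 0.10 instead, P(X ≥ 8) is 0.034 to 0.040.

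**The case against.** The strongest reply has four parts.

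**The sections may not conflict.** A reader might infer that 7.2 forbids steroid for renal flare and that 7.2.2 contradicts it outright. The text does not go that far. Section 7.2 is permissive and does not say that non-renal flare is the sole reason for starting steroid. It also lets the treating physician change immunosuppressants when necessary, which arguably includes steroid, since 7.2.2 speaks of a non-corticosteroid immunosuppressant. With the reference from 7.2.2 back to 7.2, the two can be harmonised. This stands, and limits the point to a difference in wording that sites could resolve either way.

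**The SAP may settle the scoring.** A reader might infer that the trial has no rescue rule. The documents show only that the supplied text has none. This also stands.

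**The effect may be small.** A reader might infer that the false-positive rate is materially inflated. That is not established: the rescue inputs are invented, some may be high, and no alpha is stated. At the midpoint P(X ≥ 8) stays just under 5%, because the exact test is conservative. The shift from 7 to 8 responders would follow from any one-patient change at this sample size.

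**Steroid use will be visible, and scoring is an estimand choice.** Concomitant medication is collected at each visit and change in steroid use is a secondary endpoint. That describes exposure but does not reclassify a responder. Keeping rescued patients as observed is a legitimate choice if it is stated; here it would arise by default.

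It would also be too strong to say that PRR has no protection. Its medication condition might be read to cover steroid, but does not clearly do so.

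**Conclusion.** The point holds in limited form. For Phase 2 patients not on steroid at entry, 7.2 and 7.2.2 differ in wording on renal flare, and under the supplied text a patient rescued with steroid for a renal flare can be a primary-endpoint responder in an uncontrolled test against 20%. The direction is upward relative to scoring rescue as non-response. The size is unknown: the firm statement is what one patient does to the p-value at n = 20, and the frequency figures are illustrations on assumed inputs. The conclusion about scoring depends on the SAP being silent, which could not be checked. The conclusion about wording does not, because sites act on the protocol. This is a change that should be made because it is cheap and removes an avoidable ambiguity; it does not show that the planned test is invalid.

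**What to change.** 1. In Section 7.2.2, limit the exception for adding steroid to non-renal SLE flare, matching 7.2.
2. In Section 11.1.2 or the SAP, count as a non-responder for the primary endpoint, PRR and CRR any patient whose systemic corticosteroid is started, or raised above the baseline dose, before the Week 25 UPCR for a renal flare or for a flare not documented as non-renal. Take the indication from the concomitant-medication record. Adverse event data cannot supply it, because Section 10.4 keeps non-serious lupus worsening out of the AE record.
3. Add one sensitivity analysis counting any flare-related systemic steroid start or increase above baseline before Week 25 as non-response.

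The cost is a few sentences, one table and, if the eCRF does not already capture it, one indication field. No extra patients or visits are needed. The responder rate may be slightly lower. If the SAP already scores rescue as non-response, only item 1 is needed. While 7.2.2 is open, its dose-change paragraph could also be squared with the increase for non-renal flare that 7.2 permits; that is a secondary drafting matter.

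### In Phase 2, Sections 7.2 and 7.2.2 give sites different rules on changing immunosuppressants, and the protocol's primary endpoint has no condition on such changes

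*Combined protocol and SAP*

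**What the plan says.** **Section 7.2** (SLE disease-related concomitant medications) has one bullet covering immunosuppressants and antimalarials. It says that these "agents should be continued at a stable dose except when change is deemed necessary by the treating physician or clinical investigator". The same bullet then adds a second ground for change and a pointer to the later section: "or if access is limited due to supply issues (see also Section 7.2.2"). The lead-in says SLE therapy continues "as outlined in Inclusion/Exclusion Criteria (Section 5.2), this section (Section 7.2), and Table 3". Table 3 is the Phase 2 list of permitted lupus nephritis drugs. The two bullets that follow are labelled Phase 1b and Phase 2; this one has no label.

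**Section 7.2.2**, under its Phase 2 label, says "During the study, dose modification is not permitted except for reasons of documented toxicity or unavailability", with two further exceptions: up-titration after EuroLupus CYC and the corticosteroid taper. It also says immunosuppressants "should not be added to current regimen except as above after completion of a EuroLupus CYC regimen". Its opening sentence for Phase 2 refers back to Section 7.2.

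**Corticosteroids.** Section 7.2: "Prednisone (or other corticosteroid) can be initiated or increased to treat a non-renal SLE flare". Section 7.2.2: "Corticosteroids should not be added during the study except when needed to treat an SLE flare".

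**Endpoint and test.** Sections 11.1.2 and 11.3.5 define the primary endpoint by a 50% UPCR reduction at 24 weeks and attach no condition on medication. Partial and complete renal response (PRR, CRR) do require that no prohibited medication was used. Section 11.3.5 tests the primary rate with an exact binomial test against a null of 20% or less, and leaves details to a separate SAP. Section 11.3.1 gives that SAP precedence over the protocol. Its text is not part of the supplied document.

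**The concern.** Suppose a patient's proteinuria is not improving at Week 12 and the physician wants to raise mycophenolate. Under 7.2 this is allowed; under 7.2.2 it is a deviation. Two sites can treat the same patient differently, and each can point to the protocol.

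If the dose is raised and UPCR has halved by Week 25, the endpoint as written counts the patient as a responder. Phase 2 is open-label with a single arm, so no control group shows what the extra immunosuppression did alone, and the response is credited to KZR-616. Section 2.5 expects pivotal studies to follow from the Phase 2 safety and efficacy results.

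**Working it through.** **Step 1. Do the two rules conflict?**

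| Change in a Phase 2 patient | Section 7.2 | Section 7.2.2 |
|---|---|---|
| Raise an immunosuppressant for inadequate renal response | Allowed if judged necessary | Not allowed |
| Add an immunosuppressant for inadequate renal response | Allowed if judged necessary | Not allowed |
| Change for lack of supply | Allowed | Allowed |
| Dose change for documented toxicity | Allowed if judged necessary | Allowed |
| Up-titrate after EuroLupus CYC | Allowed if judged necessary | Allowed |

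The first two rows conflict. The 7.2 bullet cannot be confined to Phase 1b: it has no phase label, its neighbours do, and its lead-in cites the Phase 2 table. The cross-references run both ways and neither uses precedence wording.

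**Step 2. Does another part of the protocol say how such a patient is scored?**

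- Sections 11.1.2 and 11.3.5: no medication condition on the primary endpoint.
- PRR and CRR condition: it excludes prohibited medication. Appendix E does not list mycophenolate, azathioprine or the calcineurin inhibitors, and Table 3 permits them with no maximum dose. Raising or adding one is not clearly prohibited medication.
- Section 9.2: "Patients may stop study drug for any of the following reasons", one of them being use of therapy that is not permitted. It does not say how the patient is scored, and 7.2 and 7.2.2 differ on what is permitted.
- Section 11.3.6: deals with withdrawals and missing data only.

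Read literally, the protocol counts the patient by observed UPCR.

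**Step 3. What can one patient do to the test?** The protocol states no alpha, power or success threshold, so there is no design figure to reproduce. Inputs: n = 20 (Section 5.1) and a null rate of 0.20 (Section 11.3.5). With X ~ Binomial(20, 0.20):

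- P(X ≥ 7) = 0.0867
- P(X ≥ 8) = 0.0321
- P(X ≥ 9) = 0.0100

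At an assumed one-sided 0.05 the threshold is 8 of 20. Rescoring one of 8 responders leaves 7, and p moves from 0.032 to 0.087. At an assumed one-sided 0.025 the threshold is 9, and rescoring one gives 8 with p = 0.032, which no longer passes.

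**Step 4. Illustration only.** Suppose KZR-616 adds nothing, m of the 20 patients are intensified and respond with probability q, and the rest respond at 0.20. Then X = Binomial(m, q) + Binomial(20 − m, 0.20). Values of P(X ≥ 8):

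| q | m = 1 | m = 2 | m = 3 | m = 4 |
|---|---|---|---|---|
| 0.20 | 0.0321 | 0.0321 | 0.0321 | 0.0321 |
| 0.25 | 0.0344 | 0.0367 | 0.0391 | 0.0417 |
| 0.35 | 0.0388 | 0.0465 | 0.0553 | 0.0654 |
| 0.50 | 0.0454 | 0.0629 | 0.0854 | 0.1133 |

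Both m and q are assumptions. The planned steroid taper could push UPCR the other way and is not modelled.

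**The case against.** **The specific rule governs the general one.** Section 7.2 is a general default pointing to 7.2.2, and 7.2.2 is the detailed Phase 2 rule. Many readers would follow 7.2.2. That is a reasonable reading, but the protocol does not state it, and 7.2.2 refers back to 7.2. A site that relies on the physician-judgement exception is also following the text.

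**The steroid rules.** A reader might infer that these contradict each other as well, because 7.2 allows an increase for a non-renal flare and the dose-modification exceptions in 7.2.2 name none. The documents do not support that. The Phase 2 part of 7.2.2 brings in Section 7.2, both sections provide for treating a flare, and a site can follow both. Only a wording clarification is needed.

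**The SAP may already hold the rule.** A reader might infer that the trial has no counting rule at all. That cannot be concluded: the separate SAP was not supplied and takes precedence. This stands, and it limits the counting half of the point. It does not reach the prescribing half, because an SAP cannot tell sites what they may prescribe.

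**Scoring regardless of therapy is a legitimate choice.** It is, if stated as such. Here it follows only from the absence of a condition, and in a single-arm test it credits rescue treatment to the study drug.

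**The word may in Section 9.2 proves little.** Agreed: the same list includes pregnancy, for which Section 10.3 requires stopping. The point does not rest on that word. Stopping study drug is not a scoring rule.

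**Any test with 20 patients turns on one patient, and Section 11.4 says the study is not powered by hypothesis testing.** Both are true. The first shows sensitivity, not a measured bias. The second does not remove the test that Section 11.3.5 specifies.

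**Conclusion.** The point holds for immunosuppressants. In Phase 2, 7.2 permits what 7.2.2 bars, neither has precedence, and the protocol's primary endpoint would count a patient intensified for inadequate renal response, subject to the unseen SAP.

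The firm figure is that one patient separates p = 0.032 from p = 0.087, which decides the result if alpha is one-sided 0.05. A reader might take 0.113 from the illustration as the true false-positive rate. It is not: it needs 4 of 20 patients intensified and a 50% response among them, neither of which comes from the documents. At 25% the range is 0.034 to 0.042, and at 20% there is no inflation. This should be corrected, but it does not show that the result will be biased by any particular amount.

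**What to change.** 1. In Section 7.2, limit the physician-judgement exception to Phase 1b and state that 7.2.2 governs Phase 2 through Week 25.
2. As a clarification only, align the steroid wording in 7.2.2 with 7.2, so that a start or increase is allowed for a non-renal SLE flare.
3. State that needed treatment is never withheld. Then state that any of the following before the Week 25 sample counts as non-response for the primary endpoint, PRR, CRR and UPCR ≤ 0.5 at 24 weeks: an immunosuppressant added, an immunosuppressant raised above its baseline dose, or a steroid started or increased for renal disease.
4. Exempt the changes that 7.2.2 leaves room for: the regimen after EuroLupus CYC, a like-for-like replacement for unavailability or toxicity, and a return to the baseline dose after a toxicity reduction or supply gap. Without these exemptions the rule would fail patients who were not intensified.
5. Report observed UPCR regardless of therapy as a sensitivity analysis. Carry the rule into the SAP, or cite the SAP rule in Section 11.1.2 if one exists.

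**Cost.** Mostly wording. Section 7.2 already has concomitant therapy recorded to the last follow-up visit, but it does not say that the reason for each change is recorded. That reason (renal or non-renal) must be captured for every immunosuppressant or steroid change. The observed response rate may fall slightly.
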